Aim 2a. Power analyses to support the sample size for the effectiveness analyses for our primary, secondary, and intermediary outcomes (see Figure 1) were conducted using G-Power 3.1. Power was set to .80 and $\alpha=.05$. Component A of the study will provide incidence rates which will be used to recalculate power prior to the implementation of Component B. For the purposes of this proposal, we calculated the MDES based on the proposed sample size. For the primary outcome of CSEC perpetration, there are no reliable incidence estimates in the literature on which to draw. With a sample size of 7,241 students enrolled, assuming conservative minimum incidence rates of CSEC perpetration of 1% to 5% (although we hypothesize it will be higher), we have power to detect an MDES difference between conditions, odds ratio (OR)=.49 to .75, respectively. Similarly, for secondary outcomes of CSEC victimization, we estimated a range of incidence rates from a conservation 5% to 50%+ based on literature discussed following for other types of victimization^{96, 132, 133} as well as rates of CSEC youth at increased risk (e.g., system involved, homeless)¹⁸⁻²⁰, which will be present in our sample based on DMPS data, we have the power to detect an MDES difference between conditions, odds ratio (OR)=.75 to .88, respectively. For secondary outcomes of TDV/SV perpetration and victimization, given past 12- months incidence rates¹³² (from nationally representative data from youth) of 63% for perpetration (of any type of TDV) and 69% for victimization (of any type of TDV), we have power to detect an MDES difference between conditions, odds ratio (OR)=.88 to .89. For sub-types of TDV (past 12-month incidence rates: physical victimization: 18%; sexual victimization: 18%; psychological victimization: 66%; physical perpetration: 12%; sexual perpetration: 12%; psychological perpetration: 62%)¹³², we have power to detect an MDES difference between conditions, odds ratio (OR)=.83 to .89, respectively. For the secondary outcome CSEC bystander action and opportunity and intermediary outcomes (i.e., knowledge, valuing of self and others, healthy relationship skills, bystander efficacy, perceptions of school social norms, prevention conversations with school personnel), the ANCOVA routine suggested power (.80) to detect a small difference between groups (MDES $d=.06$).

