Aim 2b. For the mediation analyses, based on simulation literature^{134, 135}, a sample size of 7,241 provides power ($> .80$) to detect small effects ($a=.28$; $b=.14$), which are typical of mediation designs. For the moderation analyses, we used simulation-based approach to power analysis using Mplus¹³¹. We used a multiple group model, assuming categorical moderators (e.g., gender). The proposed sample size provides sufficient power ($> .80$) to detect moderation group differences in treatment effects, $b=.20$. As an alternative way to examine power for moderation of treatment effects, we examined the MDES within moderation groups. For this analysis (G-Power ANCOVA), we took a conservative approach and used the moderator that may have the largest discrepancy in group size, such as gender identity and sexual orientation. Based on population data, we estimate 2.5% will identify as a gender minority (inclusively defined, e.g., trans, non-binary, gender queer, Two Spirit)¹³⁶⁻¹³⁸, leaving a sample size of $n=181$; and 10% of the sample will identify as a sexual minority^{113, 139}, leaving a sample size of $n=724$. Simulation power analysis supports being able to detect a small condition group difference, MDES $d=.20$.

Aim 2c. N/A

Aim 2d. N/A

Aim 2f. N/A

Proposed Analyses

Aim 1a. N/A

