We will test the hypotheses related to examining effectiveness of participation in the RTS in leading to reductions in CSEC perpetration (primary outcome), as well as reductions in CSEC victimization and TDV and SV victimization and perpetration and increases in bystander intervention in CSEC situations (secondary outcomes). To improve the rigor of analyses for Aim 2a, we will use propensity-score analysis to reduce the impact of selection bias, and latent constructs, when possible, to reduce measurement error, reduce paths and variables, and increase statistical power (MacCallum et al., 1996). This approach produces rigorous estimates of causal effects within the context of quasi-experimental designs when random assignment is not possible by controlling confounders, including selection effects¹⁴⁴. This approach will use four analytic steps: (1) estimate propensity scores in a separate analysis, (2) use the propensity scores to adjust for confounding, (3) assess balance, and (4) estimate the propensity score-adjusted treatment effects (Lanza et al., 2013). In step 1, to estimate the propensity score, we will consider all pertinent confounders and covariates (see Measurement Table 3). This step will use logistic regression of condition on the potential confounders to obtain each student's propensity score. All measured confounders that are predictive of selection into the experimental conditions and the outcomes will be included in the propensity model. Standardized mean differences in covariate values across treatment and comparison conditions will be used to determine the final set of confounders to include in estimating the propensity score. In step 2, an initial treatment effect model is estimated that adjusts for confounding using the propensity score. We will use inverse probability weighting (IPTW) to adjust for confounding. The standardized mean differences between experimental groups are computed on the weighted sample included the IPTW-adjusted propensity score (Step 2). If IPTW does not provide optimal balance, then other methods will be considered (e.g., matching). Then Step 3 is used to determine balance on the potential confounders included in the propensity score across the experimental groups. The goal is to determine whether there are any differences remaining on the confounders between experimental groups (balance = standardized mean differences $< |0.2|$ after adjustment). Confounders will be adjusted and the propensity score model (Step 1) will be re-estimated until balance is reached. Once balance is determined, the outcome analysis will be conducted in Step 4 via SEM. The experimental effect of interest will be the Average Treatment Effect (ATE), which is the population-level average effect of condition on the primary and secondary outcomes as detailed in the logic model. The effects of interest quantified are differences between experimental conditions at post-test and follow-up on outcomes (for continuous measures), the propensity score as a covariate. These effects indicate whether the outcomes in the experimental condition differ significantly from those in the comparison condition. At post-test and follow-up, we expect the difference between the experimental conditions to be significantly greater than zero, reflecting better outcomes for those in the RTS program as compared to those in the wait-list condition, after adjusting for the

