
propensity score. For categorical variables, logistic regression will be used to examine differences in prevalence by condition. The experimental condition is the independent variable in these models. Multilevel modeling is not possible given the small number of schools; thus, school will be included as a covariate. Classroom will be used as a cluster variable to adjust the standard errors for nesting. Models for Step 4 will be evaluated for overall model fit via χ^2 statistic, RMSEA :s .08, SRMR :s .10, and CFI \geq .90. We will evaluate our hypotheses across several indicators, including significance (p), confidence intervals, and the standardized difference between groups (d), as well as the directionality of included path coefficients, and odds ratios.

Mediation and Moderation Analyses (Aim 2b).

We will assess mediators (e.g., perceptions of norms intolerant of CSEC) and demographic moderators (e.g., gender) of program effectiveness, including the propensity score and school as covariates in all models. To test for mediation, we used the product of coefficients method using bias-corrected bootstrapping with 1000 resamples to calculate the confidence intervals¹⁴⁵ (MacKinnon, 2012). For our moderators (e.g., age, gender, racial groups, sexual orientation), we will estimate structural equation multiple group models, first allowing estimation of the path coefficients to vary freely across groups, and then constraining paths to be equal when a structural path coefficient of interest was significant for one group and not the other group. We will conduct model comparisons using the chi-square (χ^2) difference test (i.e., χ^2 , $p < .05$ indicating moderation).

Aim 2c. Descriptive statistics will be used to examine the extent to which sessions were delivered with fidelity. Process observations will be analyzed using thematic analysis as described above for Aim 1b.

Aim 2d. Descriptive statistics will be used to examine the frequency of responses to close-ended questions (e.g., To what extend did you like the session today?). Open-ended questions will be analyzed using thematic analysis as described above for Aim 1b.

Aim 2e. Interview data will be analyzed using thematic analysis as described above for Aim 1b.

Aim 2f. The purpose of this aim is to determine costs associated with the program implementation to inform future economic evaluation of the RTS. The process for documenting costs are described in Section C.18.

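### Aim 2b counts any moderator test below .05 as moderation, for an open list of at least four moderators, with no family control and no exploratory label

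*SAP*

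**What the plan says.** The SAP, Mediation and Moderation Analyses (Aim 2b), introduces the moderators with an open list: "For our moderators (e.g., age, gender, racial groups, sexual orientation), we will estimate structural equation multiple group models". Paths are first free to differ between groups. The SAP continues: "then constraining paths to be equal when a structural path coefficient of interest was significant for one group and not the other group". That condition acts as a gate, because a path is compared across groups only if it passes.

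The decision rule follows: "We will conduct model comparisons using the chi-square" difference test, with "p < .05$ indicating moderation".

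The SAP, Power Analyses, Aim 2b, treats moderation as a powered comparison: "The proposed sample size provides sufficient power ($> .80$) to detect moderation group differences in treatment effects".

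The outcomes are in the SAP, Outcome Analyses (Aim 2a): "reductions in CSEC perpetration (primary outcome), as well as reductions in CSEC victimization and TDV and SV victimization and perpetration and increases in bystander" intervention. Effects there are "differences between experimental conditions at post-test and follow-up on outcomes". The moderation paragraph does not say which of these outcomes or time points are to be moderated.

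Neither document names a leading moderator, a testing order or a multiplicity adjustment for Aim 2b. The SAP calls one impact analysis exploratory, the Aim 1e pilot analysis. The protocol ticks an exploratory design, but that application covers only the Phase I focus groups and cognitive interviews.

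**The concern.** The threshold of .05 is a per-test rate. With at least four moderators and no control over the family, the chance that at least one of them crosses it by luck is well above .05. The open list also allows moderators to be added after results are seen.

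A moderation claim here says that the programme works differently by age, gender, racial group or sexual orientation. Such a claim is easily repeated as a finding, and the plan gives its reader no signal that it may be one chance result among several tests. The Aim 2a comparison on the primary outcome is not affected.

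**Working it through.** The documents give no familywise error figure, so there is none to reproduce.

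**Inputs from the SAP.** Per-test threshold .05; four named moderators; the gate; N = 7,241; planning power .80; gender minority 2.5% (n = 181) and sexual minority 10% (n = 724).

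**Assumptions, not in the documents.** No true moderation; two groups per moderator; near-independent moderators; one time point; the subgroup shares and outcome correlations shown below.

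**Step 1, without the gate.** Four independent tests at .05: 1 − .95^4 = .185.

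**Step 2, with the gate, primary outcome.** For a moderator whose first group has share p, let C ~ N(θ, 1) be the full-sample z for the programme effect and D ~ N(0, 1) the z for the between-group difference. The group z-values are

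- z1 = √p·C + √(1−p)·D
- z2 = √(1−p)·C − √p·D

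A false claim needs exactly one of |z1|, |z2| above 1.96 and also |D| > 1.96 (the 1-df chi-square difference test). θ = 2.8 (1.96 + 0.84) is the 80%-power level. With a 50/50 split the per-test rate is 3.1% at θ = 0 and 4.9% at θ = 2.8. Chance of at least one false claim over four moderators, from 100,000 simulated trials per cell:

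| θ | shares .5/.5/.5/.5 | .5/.5/.3/.1 | .5/.3/.1/.025 |
|---|---|---|---|
| 0 | 12% | 12% | 14% |
| 1.5 | 16% | 16% | 15% |
| 2.8 | 18% | 17% | 14% to 15% |
| 4.5 | 13% | 12% | 11% |
| 6 | 4% | 7% | 8% |

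At θ = 6 both groups are usually significant, so the gate seldom opens. If both time points were tested (assumed correlation .5), the rate up to θ = 2.8 would be about 21% to 31%.

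**Step 3, rare binary outcome.** Binomial data at the SAP's 1% to 5% incidence, no programme effect, and a likelihood-ratio moderation test. If likelihood-ratio tests also open the gate, the rate is about 12% to 16%. If Wald tests within groups open it, the rate is about 8% to 10% at 1% incidence with the two unequal sets of shares, and about 12% to 13% in the other cases. The SAP does not say which test decides significance within a group.

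**Step 4, if all Aim 2a outcomes are moderated.** Counting TDV and SV separately gives seven outcomes: CSEC perpetration, CSEC victimization, four TDV/SV outcomes and bystander action. That is 4 × 7 = 28 tests. Pooling TDV with SV, as the Aim 2a power text does, gives five outcomes and 4 × 5 = 20 tests. Gated rule, 50/50 splits, θ from 0 to 2.8:

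| outcomes | correlation .5 | correlation .7 |
|---|---|---|
| 5 | 40% to 55% | 35% to 47% |
| 6 | 45% to 60% | 38% to 51% |
| 7 | 50% to 64% | 41% to 53% |

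With θ = 6 on every outcome these fall to about 13% to 19%.

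**Step 5, with a Holm family of four.** The first step tests at .05/4 = .0125. For four independent true nulls the familywise rate is 1 − (1 − .0125)^4 = .049.

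**The case against.** The strongest reply is that Aim 2a carries the effectiveness question, that nothing in the SAP calls moderation confirmatory, and that a power statement does not make it so. Familywise control would then be a matter of preference, and one sentence labelling moderation exploratory would be enough. Much of this stands, and the main fix below is that sentence. It does not remove the point, because the SAP gives an explicit rule for declaring moderation and no label that softens it. The Aim 2a statement that hypotheses are assessed on several indicators is not a multiplicity rule, and the moderation paragraph has its own threshold.

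Three limits on size also stand:

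- The number of tests is not given. The moderation paragraph speaks of paths of interest, Aim 2a prefers latent constructs partly to reduce paths, and the figure and table that may define the paths are not in the available text.
- A very strong common effect closes the gate for large groups and pulls the rate down.
- At 1% incidence the rate can be nearer 8%, depending on the test that opens the gate.

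A reader might infer that a false moderation claim is more likely than not somewhere in the results. The documents do not support that as a general statement: it needs a test count and an outcome correlation that the SAP does not give, and the range in step 4 runs from 35% to 64%. A reader might also infer that moderator results will decide who is offered the programme. No passage says so. The protocol (Purpose, Methods & Procedures, item 2) ties dissemination to the programme being found effective overall.

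**Conclusion.** The point holds as a stated decision rule with inflated error. On the primary outcome at one time point, with four nearly independent moderators and no true moderation, at least one false moderation claim is expected in about 12% to 18% of trials for common effects up to the 80%-power level. That is 2.4 to 3.6 times .05 (.12/.05 and .18/.05). It is less for a very strong common effect, and can be about 8% when the outcome is rare and Wald tests open the gate.

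The wider figure of 35% to 64% is conditional on applying the rule to 5 to 7 Aim 2a outcomes with correlation .5 to .7. It shows what the wording permits, not what the SAP prescribes. The change is a cheap improvement to Aim 2b and leaves the primary comparison untouched.

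**What to change.** Before outcome data are seen, replace the open moderator list in Aim 2b with a closed one and add wording such as:

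*Moderation analyses are exploratory. For every moderator tested, group-specific effects and the interaction estimate are reported with confidence intervals. Moderation is not declared on an unadjusted p-value below .05.*

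If the sponsor wants a confirmatory moderation claim, Aim 2b should name its outcome, time point and moderators in advance and apply Holm's procedure across them at overall alpha .05. The SAP gives post-test and follow-up equal standing, so the choice of time point belongs to the sponsor.

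No new data are needed, only SAP wording and the reporting of interaction estimates. The price is fewer or weaker moderation claims. Power would be low for any Holm-tested moderator with a small subgroup on a rare outcome: the gender-minority group of 181 would have about 181 × .01 = 1.8 to 181 × .05 = 9 events across both arms at 1% to 5% incidence, tested at .0125 at the first step of a family of four. The exploratory label does not lower the chance that some test crosses .05; it stops that result from being presented as established moderation.

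### The SAP tests moderation only when the path is significant in one group and not the other, so large differences between groups can go untested

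*SAP*

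**What the plan says.** The SAP section Mediation and Moderation Analyses (Aim 2b) sets out the procedure in three steps.

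- The multiple-group model is fitted, "first allowing estimation of the path coefficients to vary freely across groups".
- The equality constraint follows under a condition: "then constraining paths to be equal when a structural path coefficient of interest was significant for one group and not the other group".
- The two models are then compared: "We will conduct model comparisons using the chi-square" difference test, with p below .05 taken as moderation.

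The list of moderators reads "For our moderators (e.g., age, gender, racial groups, sexual orientation", given as examples.

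Under Power Analyses, Aim 2b, the SAP claims power above .80 "to detect moderation group differences in treatment effects" of b=.20. That claim rests on a multiple-group simulation with categorical moderators. It does not say that the test is run conditionally, and it gives neither the group sizes nor the pair of effects that was simulated.

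**The concern.** A difference in significance says little about a difference in effect. Two groups can both have clearly significant effects that differ by a wide margin or point in opposite directions. In either case the condition is not met, the constrained model is not fitted and no comparison is made.

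The condition is also worded for two groups. Racial group and age can have more than two levels, and the SAP does not say what the rule means for them.

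Aim 2b asks for whom the program works. Under this rule a null moderation result may mean only that no test was run, yet a reader could take it as evidence of uniform benefit. The more consistently the program works, the more often both groups are significant and the less often moderation is examined.

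**Working it through.** **Inputs from the SAP.** Total N 7,241 (Power Analyses, Aim 2a). Difference b=.20, stated power above .80, and a sexual-minority subgroup of 724 (Power Analyses, Aim 2b). Significance level .05.

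**Assumptions not in the documents.** Outcome SD 1, 1:1 allocation within each group, two equal groups (3,620 and 3,621) unless stated, independent students unless a design effect is given.

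**Step 1: the plan's own figure.** With half of each group per arm, SE of a group effect = 2/√n = 2/√3,620 = .0332. SE of the difference = .0332 × √2 = .0470. Expected z = .20/.0470 = 4.25. Power = Φ(4.25 − 1.96) = 98.9%. This agrees with the stated figure of above .80 for an unconditional test. With a 724/6,517 split the same formula gives 72%. The SAP does not give its split, so its figure cannot be confirmed in general.

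**Step 2: one case by hand.** For effects of .30 and .10 the expected group z-values are .30/.0332 = 9.0 and .10/.0332 = 3.0. The first is always significant. The second is non-significant with probability Φ(1.96 − 3.01) = .147. The test is therefore run in about 15% of trials, although the expected z for the difference is 4.25 (p about .00002).

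**Step 3: simulation.** There were 2,000,000 draws per scenario. Moderation is declared under the SAP rule if exactly one group has |z| > 1.96 and the difference has |z| > 1.96.

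| Effects (difference .20) | SAP rule | Always tested |
|---|---|---|
| .20 and 0 | 94% | 98.9% |
| .25 and .05 | 68% | 98.9% |
| .30 and .10 | 15% | 98.9% |
| .40 and .20 | about 0% | 98.9% |
| +.10 and −.10 | 25% | 98.9% |

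With the difference held at .20, power under the rule is 90% when the weaker effect is ±.02 and 76% to 77% when it is ±.04. It stays above .80 only if one effect lies within about .03 of zero.

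**Step 4: false positives.** With no effect in either group the rule declares moderation 3.1% of the time, against 5.0% if always tested.

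**Step 5: clustering.** The SAP gives no design effect, so a range is shown.

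| Design effect | Effects | SAP rule | Always tested |
|---|---|---|---|
| 2 | .20 and 0 | 82% | 85% |
| 2 | .30 and .10 | 43% | 85% |
| 2 | .40 and .20 | 1% | 85% |
| 3 | .30 and .10 | 52% | 69% |

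**Step 6: unequal groups (724 and 6,517).** Minority .50 and majority .20: about 0% against 97%. Minority 0 and majority .20: 70% against 72%.

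**Step 7: binary outcomes.** The SE of the log odds ratio comes from the cell counts, and the stated incidence is taken as the comparison-arm rate. The incidences are from Power Analyses, Aim 2a; the pairs of odds ratios are illustrative.

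| Incidence | OR pair | SAP rule | Always tested |
|---|---|---|---|
| 1% (primary) | .49 and .75 | 11% | 12% |
| 5% (primary) | .60 and .90 | 40% | 41% |
| 5% (primary) | .49 and .75 | 34% | 41% |
| 5% (primary) | .40 and .70 | 35% | 58% |
| 18% (secondary) | .60 and .90 | 74% | 88% |
| 18% (secondary) | .49 and .75 | 12% | 88% |

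**The case against.** **Size of effects.** The large losses need large effects. Under Aim 2a the plan is powered for d=.06 on continuous outcomes and for odds ratios of .83 to .89 on dating-violence sub-types. With smaller effects in the same equal-group model, the SAP rule against an unconditional test gives 38% against 40% (.12 and .04), about 50% against 57% (.15 and .05) and 69% against 72% (.12 and 0). At 18% incidence, odds ratios of .70 and .95 give 65% against 67%. The odds ratios of .49 and .75 used above at 18% are the plan's detectable values for 1% and 5% incidence, not for 18%. All this stands: in that range the rule costs a few points and low power is the main limit. But those are minimum detectable effects, and the plan's own moderation target is a difference of .20.

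**Neither group significant.** Here the observed gap is bounded by 1.96 × (SE1 + SE2): .13 SD for equal groups and .19 for 724/6,517. This is correct, so unlimited differences are missed only when both groups are significant. With equal SEs the untested difference can still reach z = 1.96 × √2 = 2.77 (p = .006).

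**Clustering.** A larger design effect narrows the loss for .30 and .10: at 5 it is 44% against 48%. This is so because overall power has fallen, and the .40 and .20 case remains poor.

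**The power claim.** The SAP does not state the pair of effects, so its figure is not contradicted outright; it holds under the rule for .20 and 0. It does not hold generally for a difference of .20.

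**Reading.** That the test is run only under this condition is an inference. It is the plain one, because no other constrained model is described.

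**Conclusion.** The concern holds. As written, the SAP leaves moderation untested whenever the groups agree on significance, and no other moderation test fills the gap. At the plan's own difference of .20, under the equal-group, SD 1, design effect 1 assumptions, the stated power survives only if one group's effect is close to zero; otherwise power can fall from 98.9% to 15% or to nearly nothing. The loss is small when one group has almost no effect, when both effects are small, or for the primary outcome at 1% incidence. The rule cannot produce more moderation claims than an unconditional test would, and the Aim 2a effectiveness tests are not touched. The plan should be changed, but the trial's main conclusion does not depend on it.

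**What to change.** In Mediation and Moderation Analyses (Aim 2b), delete the significance condition. For every pre-specified moderator and treatment path, compare the free and equality-constrained models with the chi-square difference test, whatever the within-group p-values. Use an omnibus test where a moderator has more than two groups, and say how age is categorised. Report the between-group difference in effect with its confidence interval. In Power Analyses, Aim 2b, state that the moderation power refers to this unconditional test, and give the group sizes assumed.

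The cost is one sentence in the analysis section, a short addition to the power section, and no new data. More comparisons will be run: four example moderators × at least five primary and secondary outcomes × two time points is about 40 tests before intermediary outcomes. They should be labelled exploratory or adjusted for multiplicity.
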